11.4. Follow-up of Subjects after Adverse Events

11.4.1. Investigator Follow-up

The Investigator should follow each AE until the event has resolved to baseline grade or better, the event is assessed as stable by the Investigator, the subject is lost to follow-up, or the subject withdraws consent. Every effort should be made to follow all SAEs considered related to study treatment or trial-related procedures until a final outcome can be reported.

All pregnancies reported during the study should be followed until pregnancy outcome. Pregnancy outcomes should be reported follow reporting instructions provided in Section 11.3.

11.4.2. Sponsor Follow-up

For SAEs, AESIs, and pregnancies, the Sponsor or a designee may follow-up by EDC query, telephone, fax, electronic mail, and/or a monitoring visit to obtain additional case details and outcome information (eg, from hospital discharge summaries, consultant reports, autopsy reports) in order to perform an independent medical assessment of the reported case.

11.4.3. Post-Study Adverse Events

At the EOT visit, the Investigator should instruct each subject to report to the Investigator any subsequent AEs that the subject's personal physician believes could be related to prior study treatment or study procedures.

The Investigator should notify the Sponsor of any death or SAE of concern occurring at any time after a subject has discontinued study participation if the event is believed to be related to prior study treatment or study procedures. The Sponsor should also be notified if the Investigator becomes aware of the development of cancer or a congenital anomaly/birth defect in a subsequently conceived offspring of a subject that participated in this study.

12. STATISTICAL METHODS

12.1. General Statistical Methods

Summaries will be produced for subject disposition, demographic and baseline disease characteristics, efficacy, safety, PK, and PD, as appropriate. Categorical data will be summarized by frequency distributions (number and percentages of subjects). Continuous data will be summarized by descriptive statistics (mean, standard deviation, median, minimum, and maximum). Time-to-event endpoints will be estimated using the Kaplan-Meier (KM) method. Point estimates and 95% CIs will be provided where appropriate, and estimates of the median and other quantiles, as well as individual time points (eg, 3-, 6-, and 12-month rates), will be produced.

All data will be provided in by-subject listings.

The study data will be analyzed and reported in the clinical study report (CSR) based on all subjects' data up to the time when 173 EFS events have been reached in the study. Complete details for all analyses will be provided in the statistical analysis plan (SAP).

12.2. Analysis Sets

The following analysis sets will be evaluated and used for presentation of the data:

- Intent-to-Treat (ITT) Analysis Set: All subjects who are randomized. Subjects will be classified according to the randomized treatment arm. The ITT Analysis Set will be the default analysis set for all analyses, unless otherwise specified.
- Safety Analysis Set (SAS): All subjects who received at least 1 dose of the study treatment. Subjects will be classified according to the treatment received. The SAS will be the primary analysis set for all safety analyses, unless otherwise specified.
- Per-Protocol Analysis Set (PPAS): All subjects in the ITT who have no major protocol deviations. Additional efficacy analyses may be performed using the PPAS. Rules for major protocol deviations resulting in exclusion from the PPAS will be specified in the SAP.
- Pharmacokinetic Analysis Set (PAS): All subjects who have at least 1 post-dose blood sample providing evaluable PK data for AG-120.

12.3. Disposition

A tabulation of subject disposition will be presented by treatment arm (AG-120 + azacitidine arm vs placebo + azacitidine arm), including the number randomized, the number treated, the reasons for treatment discontinuation, and the reasons for study withdrawal. Protocol deviations will be listed.

12.4. Baseline Evaluations

Demographic and baseline disease characteristic data will be summarized by treatment arm. Data to be tabulated will include sex, age, race, ethnicity, and disease-specific information.

12.5. Efficacy Analyses

During treatment, response will be evaluated by the Investigator based on modified IWG Response Criteria for AML (see Section 10.8.1) to determine subject status and continuation on study treatment. These response assessments will be used for the analysis of all efficacy endpoints. Because CRh is not part of modified IWG response criteria, it will be derived by the Sponsor.

To control the overall Type 1 error rate at the 1-sided 2.5% level, the fixed sequence testing procedure (Westfall and Krishen, 2001) will be used to adjust for multiple statistical testing of the primary and key secondary efficacy endpoints.

These endpoints will be tested in the following order:

- EFS
- CR rate
- OS
- CR + CRh rate
- ORR

No control of the alpha level will be made for the other analyses. No interim analyses for efficacy are planned.

12.5.1. Analyses of the Primary Endpoint

The analysis for the primary endpoint will be performed at the time when 173 EFS events have occurred. Event-free survival is defined as the time from randomization until treatment failure, relapse from remission, or death from any cause, whichever occurs first. Treatment failure is defined as failure to achieve CR by Week 24. Subjects who do not achieve CR by Week 24 will be considered to have had an event at Day 1 of randomization. For the remaining CR responders, the event time will be the time of either disease relapse or death, whichever occurs first. Event-free survival will be censored upon initiation of a new anticancer therapy should a new therapy be initiated prior to any EFS event.

Event-free survival will be tested using the log-rank test stratified by the randomization stratification factors (de novo status and geographic region) based on the data in the ITT Analysis Set. The basis for a claim of efficacy will be the statistical significance of EFS in favor of the AG-120 + azacitidine arm when the 1-sided $p \leq 0.025$ (observed EFS HR ≤ 0.742).

The distribution of EFS will be estimated using the KM method. The KM curves and 25th, 50th (median), and 75th percentiles (if estimable), along with their 2-sided 95% CIs, will be presented for each treatment arm. The KM estimates at individual time points (eg, 3-, 6-, and 12-month rates) will also be presented for each treatment arm. A Cox regression model stratified by randomization stratification factors will also be used to estimate the HR of EFS. However, given that the assumption of proportional hazards is not met based on the EFS definition, the overall HR is less meaningful in this context. As EFS is a composite endpoint, the estimates presented separately by each component are more meaningful: CR rate by 24 weeks and EFS among those who have achieved CR by 24 weeks. For subjects who achieve CR by 24 weeks, the KM curves

of the EFS distribution and 25th, 50th (median), and 75th percentiles (if estimable) along with their 2-sided 95% CIs will be presented for each treatment arm. A Cox regression model stratified by randomization stratification factors will also be used to estimate the HR of EFS for these subjects. In addition, the ratio of restricted mean survival time, which does not rely on proportional hazards assumptions, between the 2 arms will also be presented to summarize the treatment effect.

Sensitivity analyses will be performed to explore the robustness of the primary analysis results and will include an analysis based on the stratified log-rank test following the ITT principle, where the time of relapse or death is determined using the actual date of relapse or death without censoring for missing disease assessments or start of subsequent anticancer therapy. Additional sensitivity analyses for EFS will be prespecified in the SAP and will include:

- Stratified log-rank test using the PPAS
- Unstratified log-rank test using the ITT
- Stratified log-rank test using the ITT, where for subjects who do not achieve CR by Week 24, instead of being considered to have had an EFS event at Day 1 of randomization, the event time will be either 24 weeks or EOT, whichever is earlier.

Subgroup analyses will be performed based on the stratification factors. The analyses will include the presentation of CR rate by 24 weeks and KM estimates of EFS among subjects who achieved CR by 24 weeks, unstratified log-rank tests, and HRs (with associated 95% CIs) from unstratified Cox regression models. Other subgroup analyses for EFS, including analyses by cytogenetic risk, will be specified in the SAP.

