Event-free survival is defined as the time from randomization until treatment failure, relapse from remission, or death from any cause, whichever occurs first. Treatment failure is defined as failure to achieve CR by Week 24. Subjects who do not achieve CR by Week 24 will be considered to have had an event at Day 1 of randomization. For the remaining CR responders, the event time will be the time of either disease relapse or death, whichever occurs first. Event-free survival will be censored upon initiation of a new anticancer therapy should a new therapy be initiated prior to any EFS event. Sensitivity analyses will be performed to explore the robustness of the primary analysis results and will include an analysis based on the stratified log-rank test following the Intent-to-Treat principle, where the time of relapse or death is determined using the actual date of relapse or death without censoring for missing disease assessments or start of subsequent anticancer therapy.

No interim analyses for efficacy are planned. The analysis for the primary endpoint EFS will be performed at the time when 173 EFS events have occurred or as deemed necessary by the IDMC. Event-free survival will be tested using the log-rank test stratified by the randomization stratification factors (de novo status and geographic region). The basis for a claim of efficacy will be the statistical significance of EFS in favor of the AG-120 + azacitidine arm when the 1-sided $p \leq 0.025$ (observed EFS hazard ratio [HR] ≤ 0.742).

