The distribution of EFS will be estimated using the KM method. The KM curves and 25th, 50th (median), and 75th percentiles (if estimable), along with their 2-sided 95% CIs, will be presented for each treatment arm. The KM estimates at individual time points (eg, 3-, 6-, and 12-month rates) will be presented for each treatment arm. A Cox regression model stratified by randomization stratification factors will also be used to estimate the HR of EFS. However, given that the assumption of proportional hazards is not met based on the EFS definition, the overall HR is less meaningful in this context. As EFS is a composite endpoint, the estimates presented separately by each component are more meaningful: CR rate by 24 weeks and EFS among subjects who achieved CR by 24 weeks. For subjects who achieve CR by 24 weeks, the KM curves of the EFS distribution and 25th, 50th (median), and 75th percentiles (if estimable) along with their 2-sided 95% CIs will be presented for each treatment

arm. A Cox regression model stratified by randomization stratification factors will also be used to estimate the HR of EFS for these subjects.

It is assumed that the CR rate by 24 weeks is 20% and 40% for the placebo + azacitidine arm and the AG-120 + azacitidine arm, respectively. For subjects who achieved CR by 24 weeks, a target HR of 0.76 is assumed for EFS (equivalent to a median EFS among responders of 14.6 months in the placebo + azacitidine arm vs 19.2 months in the AG-120 + azacitidine arm, assuming an exponential distribution). Under these assumptions, a total of 173 EFS events are required to provide 80% power at a 1-sided alpha of 0.025 level of significance to reject the null hypothesis using a stratified log-rank test. Assuming a recruitment period of approximately 44 months, with an accrual rate of 3 subjects per month during the first 10 months and 5 subjects per month thereafter, along with an assumed 5% overall dropout rate, approximately 200 subjects will be randomized to the 2 treatment arms in a 1:1 ratio. Given the above assumptions, it is estimated that the analysis of the primary endpoint for EFS will occur approximately 52 months after the first subject was randomized.

Key Secondary Endpoint Analyses:

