12.12. Sample Size Estimation

A total of approximately 200 subjects with previously untreated IDH1m AML will participate in this study.

Assumptions for the placebo + azacitidine arm in this study are based on results from Study AZA-AML-001 in newly diagnosed AML patients who are ineligible for intensive IC receiving AG-120 in combination with azacitidine. Preliminary data from Study AZA-AML-001 were obtained under a data exchange agreement with Celgene. Based on results from a retrospective analysis of these data, the CR rate at 24 weeks is assumed to be 20% for the placebo + azacitidine arm. For subjects who achieve CR by 24 weeks, the median EFS is assumed to be 14.6 months. Assumptions for the AG-120 + azacitidine arm in this study are based on results from Study AG-221-AML-005 in newly diagnosed AML patients who are ineligible for intensive IC receiving AG-120 in combination with azacitidine. The CR rate by 24 weeks is

assumed to be 40%. For subjects who achieve CR by 24 weeks, a target HR of 0.76 for EFS (equivalent to a median EFS among responders of 14.6 months in the placebo + azacitidine arm vs 19.2 months in the AG-120 + azacitidine arm, assuming an exponential distribution) is assumed. Based on simulation results, the average overall HR over 10,000 simulations for the entire population is 0.641. Given that the assumption of proportional hazards is not met based on the EFS definition, the overall HR is less meaningful in this context. Therefore, the overall HR for the entire population was not part of the study design assumptions.

Under these assumptions, a total of 173 EFS events are required to provide 80% power at a 1-sided alpha of 0.025 level of significance to reject the null hypothesis using a stratified log-rank test. Assuming a recruitment period of approximately 44 months, with an accrual rate of 3 subjects per month during the first 10 months and 5 subjects per month thereafter, along with an assumed 5% overall dropout rate, approximately 200 subjects will be randomized to the 2 treatment arms in a 1:1 ratio. Given the above assumptions, it is estimated that the analysis of the primary endpoint for EFS will occur approximately 52 months after the first subject is randomized.

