6.2.2. Decision Rules

The final analysis for the primary and key secondary efficacy endpoints will be performed after all subjects have been randomized in the study and followed for a minimum of 24 weeks and the target number of events for EFS has occurred (see [Section 2](#)).

The basis for a claim of efficacy will be the statistical significance of EFS in favor of the AG-120+azacitidine arm when the 1-sided p-value <0.025. To protect the integrity of the study and to preserve the Type 1 error at or below 1-sided $\alpha=0.025$, a hierarchical testing strategy will be used as described in [Section 6.2.1](#) to test each of the key secondary efficacy endpoints and statistical significance will be achieved with 1-sided p-value <0.025 for each endpoint.

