7.7.1. Primary Endpoint

7.7.1.1. Primary Analyses for EFS

EFS is defined as the time from randomization until TF, relapse from remission, or death from any cause, whichever occurs first. TF is defined as failure to achieve CR by Week 24. Subjects who do not achieve CR by Week 24 will be considered to have had an EFS event at Day 1 of randomization. For subjects who achieve CR by Week 24 (responders), the EFS time will be the time from randomization to relapse or death, whichever occurs first.

EFS will be tested using the log-rank test stratified by the randomization stratification factors. The basis for a claim of efficacy will be the statistical significance of EFS in favor of the AG-120+azacitidine arm when the 1-sided p-value <0.025.

Kaplan-Meier estimates (product-limit estimates) will be presented by treatment arm together with a summary of associated statistics. In particular, the EFS rate at 1 day, and 3, 6, 9, 12, 18, 24 and 36 months will be estimated with corresponding 2-sided 95% CIs. The CIs for the survival function estimates at the time points defined above will be derived using the log-log transformation (conftype=loglog default option in SAS PROC LIFETEST) with back transformation to a CI on the untransformed scale. The estimate of the standard error (SE) will be computed using Greenwood's formula.

The HR will be estimated using a Cox's proportional hazards (PH) model stratified by the randomization strata. Each stratum will define a separate baseline hazard function (using the "STRATA" statement in SAS PROC PHREG), ie for the i-th stratum the hazard function is expressed as: $h(i;t)=h(i,0;t)\exp(x\beta)$, where $h(i,0;t)$ defines the baseline hazard function for the i-th stratum and x defines the treatment arm (0= control arm, 1=treatment arm) and β is the unknown regression parameter. Ties will be handled by replacing the proportional hazards model by the discrete logistic model (Ties=Discrete option in SAS PROC PHREG). Given that the PH assumption is not met based on the EFS definition, the overall HR may not be meaningful.

As EFS is a composite endpoint, the estimates for each component will be summarized:

- CR rate by 24 weeks (following the methodology outlined in Section 7.7.2.1 without presenting p-values)
- EFS among subjects who achieve CR by 24 weeks (following the methodology outlined above restricted only to subjects who achieve CR by 24 weeks without

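### The HR of 0.742 printed in the protocol's efficacy-claim sentence is not the p = 0.025 point for this EFS endpoint

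*Protocol*

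**What the plan says.** Protocol Section 12.5.1 bases the efficacy claim on significance of EFS by the stratified log-rank test at a 1-sided p of at most 0.025, followed in brackets by "observed EFS HR ≤ 0.742". The Synopsis carries the same bracket, beginning "observed EFS hazard ratio [HR".

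Section 12.5.1 also fixes the event time of treatment failures: "Subjects who do not achieve CR by Week 24 will be considered to have had an event at Day 1 of randomization".

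Both documents play down the overall HR. The Synopsis says "the overall HR is less meaningful in this context", and Protocol Section 12.12 states that "the overall HR for the entire population was not part of the study design assumptions". SAP Section 7.7.1.1 says "the overall HR may not be meaningful".

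The SAP states the decision rule without any HR. SAP Section 7.7.1.1 gives the EFS rule by p-value only, and Section 6.2.2 does the same for the key secondary endpoints: "statistical significance will be achieved with 1-sided p-value <0.025 for each endpoint". For the Cox estimate, SAP Section 7.7.1.1 specifies "Ties will be handled by replacing the proportional hazards model by the discrete logistic model (Ties=Discrete option in SAS PROC PHREG"). The protocol names no tie method.

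**The concern.** The bracket reads as a translation of the p-value threshold to the HR scale. That translation assumes information of one quarter of the event count, which needs events spread over many distinct times. This endpoint puts most events at a single time, where the log-rank variance is much smaller and the estimated HR depends heavily on how ties are handled.

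The figure therefore gives readers a benchmark that can contradict the test it accompanies. A trial reporting an HR of 0.70 from the planned model would seem to meet the printed criterion while failing the log-rank test. The protocol would also carry a figure in its success sentence that the SAP's rule does not contain.

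**Working it through.** **Inputs from the documents.** About 200 subjects, 1:1; 173 EFS events; 1-sided 0.025; CR by 24 weeks 40% vs 20%; median EFS in responders 19.2 vs 14.6 months, exponential; accrual 3 per month for 10 months, then 5 per month; 5% dropout (Protocol 12.12, SAP 6.2.1). At least 24 weeks of follow-up for all subjects (SAP Section 2).

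**1. Reproduce the plan's figure.** exp(−2 × 1.95996/√173) = 0.7423. This implies log-rank information of 173/4 = 43.25.

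**2. Information with the Day-1 tie.** Expected Day-1 events: 100 × 0.60 + 100 × 0.80 = 140. The hypergeometric variance at that time is 100 × 100 × 140 × 60/(200² × 199) = 10.55, against 140/4 = 35 if untied. The other 33 events add about 33/4 = 8.25. The total is about 18.80, and exp(−1.96/√18.80) = 0.636.

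**3. Why the tie method matters.** On Day 1 the discrete model estimates an odds ratio, about (60/40)/(80/20) = 0.375. Breslow's method gives the ratio of proportions, 60/80 = 0.75.

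**4. Simulation under the design alternative.** 3,000 trials per setting, cut at the later of the 173rd event and 24 weeks after the last subject. Assumptions, because the documents do not give them: responder dropout of 5% per 24 months; permuted blocks of 4 within stratum; strata A with 25% secondary AML and regions 10/45/10/35%; strata B with 40% secondary AML and regions 25% each. The significance point is exp(log HR × 1.96/|Z|), averaged over trials with |Z| between 1.76 and 2.16 (323, 298 and 327 trials).

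| | Unstratified | Strata A | Strata B |
|---|---|---|---|
| Events / of which Day 1 | 175.8 / 140.0 | 175.8 / 139.7 | 175.8 / 139.7 |
| Log-rank variance | 17.8 | 16.6 | 16.5 |
| Log-rank power (stated 80%) | 82.7% | 83.4% | 83.1% |
| HR at p = 0.025, Discrete | 0.637 | 0.626 | 0.622 |
| HR at p = 0.025, Efron | 0.721 | 0.727 | 0.725 |
| HR at p = 0.025, Breslow | 0.823 | 0.822 | 0.823 |
| Discrete HR ≤ 0.742 but p > 0.025 | 340 (11.3%) | 340 (11.3%) | 353 (11.8%) |
| Discrete HR > 0.742 but p ≤ 0.025 | 0 | 0 | 0 |
| Largest Discrete HR in a significant trial | 0.661 | 0.653 | 0.648 |
| Efron HR ≤ 0.742 but p > 0.025 | 4.7% | 3.7% | 4.2% |
| Efron HR > 0.742 but p ≤ 0.025 | 0.8% | 1.3% | 1.0% |

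A Discrete HR near 0.742 had a median 1-sided p of 0.095 to 0.105 (5th to 95th percentile 0.07 to 0.14).

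**5. Under the null.** The Discrete point averages 0.56 to 0.59 with CR 20% in both arms and 0.63 to 0.64 with CR 30% in both arms, so it moves with the CR rate. The 20% figures rest on only 60 to 82 near-boundary trials each.

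**6. Cross-check with other assumptions.** A second simulation used 25% secondary AML, regions 10/40/10/40%, and 5% of subjects dropping out at uniform times over 24 months. In 2,500 trials under the alternative, the Discrete point was 0.638 unstratified and 0.620 stratified, and 11.2% and 13.5% of trials had HR ≤ 0.742 with p > 0.025. In 4,000 trials per null setting, a Discrete HR ≤ 0.742 occurred in 10% to 15% of trials, against 2.1% to 2.8% with p ≤ 0.025.

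**The case against.** The strongest reply is that the bracket is harmless. The sentence rests the claim on the p-value, and the text that follows warns that the overall HR means little. With the SAP's model, no simulated trial reached p ≤ 0.025 with an HR above 0.742, so requiring both conditions gives the same decision as the p-value alone. The SAP omits the HR but does not set a different cutoff. All of this stands, and it limits the consequence.

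A second reply is that 0.742 should not be judged on the Discrete scale. The sponsor's simulated average overall HR of 0.641 matches Efron ties (0.637 unstratified and 0.644 stratified in the second simulation) and not Discrete ties (0.525 and 0.512). The planning figures therefore look Efron-type, although the documents do not say so. On that scale the significance point averages 0.72 to 0.73 and conflicts fall to between 5.0% and 5.5% of trials. This also stands, but it does not rescue the equivalence. The Efron point ranges from 0.64 to 0.81 in single trials and rises to about 0.78 to 0.79 under a null with CR 20% in both arms. The HR the SAP will report is the Discrete one.

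The cautions about the overall HR concern its interpretation under non-proportional hazards. None of them tells the reader that 0.742 is not the significance point.

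**Conclusion.** The concern holds. The figure 0.742 is a correct result of the untied-events formula, but that formula does not fit this endpoint. Under the design alternative the p = 0.025 point averages 0.62 to 0.64 with the SAP's tie handling. Discrete HRs from about 0.66 to 0.742 would appear to meet the printed figure while failing the test.

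The variance argument needs only the documents' CR rates and sample size. The simulated decimals also rest on the assumed strata, blocks and dropout process; the unstratified and stratified runs lead to the same conclusion.

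The log-rank test, type I error, power, 173-event target, sample size and SAP decision rule are unaffected. What is wrong is a threshold inside the primary success sentence. It should be corrected, but it does not threaten the formal decision.

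**What to change.** Delete the HR bracket from the Synopsis (analysis of the primary endpoint) and from Protocol Section 12.5.1. The stratified log-rank p-value then stands as the only criterion, as in SAP Sections 6.2.2 and 7.7.1.1. The existing cautions about the overall HR can stay as they are.

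The cost is two deletions at the next protocol amendment. The SAP, test, alpha, event target, sample size and tie method do not change. Readers lose a rough effect-size anchor, but the CR rate by 24 weeks, EFS among responders and the restricted mean survival time comparison are already planned. Labelling the figure as an untied-events approximation would be a weaker alternative, since it leaves a misleading number in the success sentence.
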